6.1.8 Dose Adjustments/Modifications/Delays

A missed dose of study medication may be taken later up to 8 hours before the next scheduled dose; otherwise, the missed dose should not be given.

If the parent/caregiver is unable to administer the full dose due to spillage (eg, dose was spilled during measuring, subject spit dose out during administration), he/she should attempt to give the full dose noting the extra amount used to fulfill the dose. If the subject vomits within the first 15 minutes of administration the dose may be re-administered. Care must be taken not to overdose. If the amount spilled is not known, the parent/caregiver should not give additional

Version: 11 Jan 2021

medication to avoid potential overdose.

6.1.9 Duration of Therapy

Duration of therapy will be14 weeks with extension available.

6.1.10 Tracking of Dose

The study team will assess and track subject compliance with the study drug regimen via clinical evaluations and follow-up email or phone calls.

7 Study Procedures and Schedule

7.1 Study Specific Procedures

- -Medical history: Any medical problems/conditions throughout subject's body system, relevant medical events and/or procedures/surgery
- -Medication history: complete medication history of any anti-epileptic medications; current history other prescription and over-the-counter medications.
- -Physical examination: vital signs including temperature, height and weight and organ systems to be assessed
- -Neurological examination: examination of sensory neurons, motor responses and reflexes
- -Biological specimen collection and laboratory evaluations.
- -Procedures: Doppler Echocardiography and Electrocardiograms
- -Questionnaires and seizure diary

7.2 Clinical Laboratory Evaluations

- **-Hematology:** hemoglobin, hematocrit, white blood cells (WBC) with differential count, platelet count.
- -Coagulation: Prothrombin time (PT)/International normalized ratio (INR), activated partial thromboplastin time (PTT)
- -Biochemistry: comprehensive metabolic panel, creatinine, total bilirubin, alanine aminotransferase (ALT), aspartate and aminotransferase (AST) albumin (ALB), alkaline phosphatase (AP), alanine aminotransferase (ALT; SGPT), aspartate aminotransferase (AST; SGOT), bicarbonate, blood urea nitrogen (BUN), calcium (Ca), carbon dioxide (CO2), chloride (Cl), creatinine, creatine kinase, gamma-glutamyl transferase (GGT), globulin, glucose, lactate dehydrogenase (LDH), phosphorus, potassium (K), sodium (Na), thyroid function (T3, T4, and thyroid stimulating hormone [TSH]), total bilirubin, direct bilirubin, total cholesterol, total protein, triglycerides, uric acid.

Version: 11 Jan 2021

-Urinalysis: dipstick urinalysis, including protein, hemoglobin and glucose; if dipstick is abnormal, complete urinalysis with microscopic evaluation is required.

- **-Urine or serum pregnancy test:** usually to be done within 24 hours prior to study intervention and results must be available prior to administration of study product.
- **Urine or serum THC test:** usually to be done within 24 hours prior to study intervention and results must be available prior to administration of study product.
- -Plasma Sample for Concomitant Antiepileptic Drug(s): Plasma samples to ensure that concomitant AEDs dosing is within an acceptable range will be conducted during the study as outlined.

Blood work will be about 8.0 - 20.0mL (about 2-4 teaspoons) of blood depending on the amount of concomitant medications.

If caregivers/patients are not able to travel to the NYU facility due to COVID-19 travel restrictions, clinical laboratory evaluations can be completed at a local facility.

7.3 Procedures

Electrocardiograms: Twelve-lead ECGs will be conducted during study as outlined after the subject has been in the supine position resting for ≥5 minutes. Heart rate, PR duration, QRS duration, QT duration, and the investigator's overall interpretation will be recorded.

Doppler Echocardiography: Doppler echocardiography will be conducted at the hospital facility with experience for the subject's age. If caregivers/patients are not able to travel to NYU facility, doppler echocardiography can be done at a local facility. Doppler echocardiography can be done +/- 7 days from study visit. Doppler echocardiography uses ultrasound technology to examine the heart or blood vessels. An ECHO uses high frequency sound waves to create an image of the heart while the use of Doppler technology allows determination of the speed and direction of blood flow by utilizing the Doppler effect. Predetermined standard guidelines on the proper evaluation of certain measurements, as well as abnormality thresholds, were constructed by the sponsor prior to study initiation. Readings will be sent back to site to determine the appropriate benefit is and any findings consistent with cardiac valvopathy or pulmonary hypertension.

7.4 Questionnaires

*Given the profound intellectual disability of this population (ie, adults have intelligence of <age 5), the pediatric versions will be used for both children and adults. *

- -Caregiver Global Impression of Change (CGIC). The parent/caregiver rated change on a 7-point scale: 1-very much improved; 2-much improved; 3-minimally improved; 4-no change; 5-minimally worse; 6-much worse; and 7-very much worse
- -Investigator Global Impression of Change (IGIC). The investigator rated change on a

Version: 11 Jan 2021

7-point scale: 1-very much improved; 2-much improved; 3-minimally improved; 4-no change; 5-minimally worse; 6-much worse; and 7-very much worse

- -Quality of Life in Childhood Epilepsy Scale (13). A low-burden parent/caregiver completed assessment that looks at how epilepsy affects day-to-day functioning of their child in various life areas, including physical activities, well-being, cognition, social activities, behavior and general health in comparison to other children their age,
- -Pediatric Quality of Life Inventory (PEDS-QL). A parent/caregiver completed assessment that looks at how epilepsy affects day-to-day functioning of their child in various life areas, including physical activities, well-being, cognition, social activities, behavior and general health during a specific time frame

7.5 Study Schedule

7.5.1 *Core study*

7.5.1.1 Baseline

Visit 1 Baseline (Week 0)

Baseline (Visit 1) will occur at NYU CEC. Procedures will proceed as follows:

- Obtain written informed consent/assent.
- Determine if the subject meets the preliminary eligibility criteria:
 - Collect demographic information
 - o Collect current and relevant medical history
 - Identify concomitant medications used
 - o Identify and confirm stable use AED medications

If the subject meets the preliminary eligibility criteria, the following assessments will be performed:

- Vital signs (including systolic and diastolic blood pressure, radial pulse rate, and body temperature): perform in sitting position
- Physical and neurological examination including Height and weight
- EKG and echocardiogram
- Complete the following assessments:
 - o Caregiver and Investigator Global Impression of Change
 - o OOLCE
 - o PEDS-QOL
- Blood draw for clinical laboratory evaluations:
 - Complete blood count (CBC), comprehensive metabolic panel (CMP)
 Serum/Urine human chorionic gonadotropin (HCG), as applicable (sample taken only for female subjects of childbearing potential), and antiepileptic medication levels

Study number: s18-01530 Page 19 Version: 11 Jan 2021

Urinalysis

- Urine or serum THC
- Record any AEs occurring since signing the ICF and any that occur during this visit
- Instruct subject or subject's caregiver to keep a seizure diary for the next 2 weeks, including the following information:
 - o Seizure type and duration
 - Use of rescue medications
- Dispense study drug and review administration instructions and titration schedule
- First dose given in office
- Instruct subject to return in 2 weeks for Visit 2

Safety call telephone

The safety call will occur between visit 1 and visit 2. It will proceed as follows:

- Record any AEs occurring since last visit and any that occur during this visit
- Issues with titration schedule
- Record any changes in concomitant medications

Visit 2 (Week 2)

Visit (Week 2) as follows:

- Physical and neurological examination and height and weight
- Vital signs (including systolic and diastolic blood pressure, radial pulse rate, and body temperature): performed after the subject has been in a sitting position for 3–5 minutes
- Collect seizure diary and review entries
- Record any AEs occurring since last visit and any that occur during this visit
- Record any changes in concomitant medications
- Complete the following assessments:
 - o Caregiver and Investigator Global Impression of Change
 - QOLCE
 - o PEDS-QOL
- Blood draw for Complete blood count (CBC), comprehensive metabolic panel (CMP) Serum/Urine human chorionic gonadotropin (HCG), as applicable (sample taken only for female subjects of childbearing potential)
- Urinalysis
- Urine or serum THC
- Dispense new seizure diary and review instructions for completion
- Dispense study drug and review administration instructions
- Instruct subject to return in 4 weeks for Visit 3

Version: 11 Jan 2021 Visit 3 (Week 6)

The subject will return to the site for Visit 3. Procedures at Visit 3 will proceed as follows:

- Physical and neurological examination and height and weight
- Vital signs (including systolic and diastolic blood pressure, radial pulse rate, and body temperature): performed after the subject has been in a sitting position for 3–5 minutes
- EKG and echocardiogram
- Collect seizure diary and review entries
- Record any AEs occurring since last visit and any that occur during this visit
- Blood draw for Complete blood count (CBC), comprehensive metabolic panel (CMP) Serum/Urine human chorionic gonadotropin (HCG), as applicable (sample taken only for female subjects of childbearing potential), and antiepileptic medication levels
- Urinalysis
- Urine or serum THC
- Complete the following assessments:
 - Caregiver and Investigator Global Impression of Change
 - o OOLCE
 - o PEDS-QOL
- Record any changes in concomitant medications
- Dispense new seizure diary and review instructions for completion
- Review returned study drug and compliance
- Dispense study drug and review administration instructions
- Instruct subject to return in 4 weeks for Visit 4

Safety call telephone

The safety call will occur between visit 3 and visit 4. It will proceed as follows:

- Record any AEs occurring since last visit and any that occur during this visit
- Record any changes in concomitant medications

Visit 4 (Week 10)

The subject will return to the site for Visit 4. Visit 4 will proceed as follows:

- Physical and neurological examination and height and weight
- Vital signs (including systolic and diastolic blood pressure, radial pulse rate, and body temperature): performed after the subject has been in a sitting position for 3–5 minutes
- Collect seizure diary and review entries
- Record any AEs occurring since last visit and any that occur during this visit
- Record any changes in concomitant medications
- Complete the following assessments:
 - Caregiver and Investigator Global Impression of Change
 - QOLCE
 - o PEDS-QOL

Study number: s18-01530 Page 21 Version: 11 Jan 2021

• Blood draw for Complete blood count (CBC), comprehensive metabolic panel (CMP) Serum/Urine human chorionic gonadotropin (HCG), as applicable (sample taken only for female subjects of childbearing potential), and antiepileptic medication levels

- Urinalysis
- Urine or serum THC
- Dispense new seizure diary and review instructions for completion
- Dispense study drug and review administration instructions
- Instruct subject to return in 4 weeks for Visit 5

Safety call telephone

The safety call will occur between visit 4 and visit 5. It will proceed as follows:

- Record any AEs occurring since last visit and any that occur during this visit
- Record any changes in concomitant medications

Visit 5/End of study/ End of treatment/ Withdrawal visit (Week 14)

Visit 5 will proceed as follows:

- Physical and neurological examination and height and weight
- Vital signs (including systolic and diastolic blood pressure, radial pulse rate, and body temperature): performed after the subject has been in a sitting position for 3–5 minutes
- EKG and echocardiogram
- Collect seizure diary and review entries
- Record any AEs occurring since last visit and any that occur during this visit
- Record any changes in concomitant medications
- Complete the following assessments:
 - o Caregiver and Investigator Global Impression of Change
 - o OOLCE
 - o PEDS-QOL
- Blood draw for Complete blood count (CBC), comprehensive metabolic panel (CMP) Serum/Urine human chorionic gonadotropin (HCG), as applicable (sample taken only for female subjects of childbearing potential), and antiepileptic medication levels
- Urinalysis
- Urine or serum THC
- For those subjects who have responded (response level ≥ 40%) and will like to continue in to the extension study:
 - o Dispense new seizure diary and review instructions for completion
 - o Dispense study drug and review administration instructions
 - o Instruct subject to return in 12 weeks for Extension visit 1
- For those subjects who have not responded and will not continue in to the extension study:
 - o Taper schedule will be given
 - O Subject have final post taper follow up in 4 weeks after the last dose

Version: 11 Jan 2021 7.5.2 Extension

Extension visits

If study medication provide benefit to the subject (response level \geq 40%), study medication will be provided until FDA approval or program discontinuation by Zogenix. The subject will return to the site every 12 weeks for extension visits. This includes:

- Physical and neurological examination and height and weight
- Vital signs (including systolic and diastolic blood pressure, radial pulse rate, and body temperature): performed after the subject has been in a sitting position for 3–5 minutes
- EKG and echocardiogram
- Collect seizure diary and review entries
- Record any AEs occurring since last visit and any that occur during this visit
- Record any changes in concomitant medications
- Complete the following assessments:
 - Clinical Caregiver/Investigator Global Impression of Change
 - o OOLCE
 - o PEDS-QOL
- Blood draw for Complete blood count (CBC), comprehensive metabolic panel (CMP) Serum/Urine human chorionic gonadotropin (HCG), as applicable (sample taken only for female subjects of childbearing potential), and antiepileptic medication levels
- Urinalysis
- Urine or serum THC
- Dispense new seizure diary and review instructions for completion
- Dispense masked study drug and review administration instructions
- Instruct subject to return in 12 weeks for next visit

Safety call telephone

The safety call will occur between extension visit. It will proceed as follows:

- Record any AEs occurring since last visit and any that occur during this visit
- Record any changes in concomitant medications

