	6.1.9 Duration of Therapy				
	6.1.10 Tracking of Dose				
7	7 STUDY PROCEDURES AND SCHEDULE				 16
	7.1 STUDY SPECIFIC PROCEDURES				16

Study number: s18-01530 Version: 11 Jan 2021 Page v

Version: 11 Jan 2021

List of Abbreviations

AE Adverse Event/Adverse Experience

CFR Code of Federal Regulations

CRF Case Report Form

CSOC Clinical Study Oversight Committee

DCC Data Coordinating Center

DHHS Department of Health and Human Services

DSMB Data and Safety Monitoring Board

FFR Federal Financial Report
FWA Federalwide Assurance
GCP Good Clinical Practice

HIPAA Health Insurance Portability and Accountability Act

ICF Informed Consent Form

ICH International Conference on Harmonisation

IRB Institutional Review Board
ISM Independent Safety Monitor

MOP Manual of Procedures

N Number (typically refers to participants)

NIH National Institutes of Health

OHRP Office for Human Research Protections
OHSR Office of Human Subjects Research

PI Principal Investigator

QA Quality Assurance

QC Quality Control

SAE Serious Adverse Event/Serious Adverse Experience

SOP Standard Operating Procedure

US United States

Version: 09 Sep 2020

Protocol Summary

Title	Fenfluramine in CKDL5 Deficiency Disorder (CDD)		
Brief Summary	We will enroll 10 patients, ages 2-35 years old, with a confirmed genetic/clinical diagnosis of CDKL5 Deficiency Disorder (CDD) in an open label trial of fenfluramine for seizure control. Protocol – patients will be titrated over 14 days to a dose of ZX008 0.8 mg/kg/day (maximum dose 30 mg/d)		
Phase	NA		
Objectives	Decrease in seizure frequency and change in impression and quality of life		
Methodology	Open label		

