3.2 Secondary Objectives

- Caregiver/Investigator Global Impression of Change (C/IGIC). The parent/caregiver and investigator rated change on a 7-point scale: 1-very much improved; 2-much improved;
 3-minimally improved; 4-no change; 5-minimally worse; 6-much worse; and 7-very much worse
- Quality of Life in Childhood Epilepsy Scale . A low-burden parent/caregiver completed assessment that looks at how epilepsy affects day-to-day functioning of their child in

Version: 11 Jan 2021

various life areas, including physical activities, well-being, cognition, social activities, behavior and general health in comparison to other children their age,

 PEDS-QL. A parent/caregiver completed assessment that looks at how epilepsy affects day-to-day functioning of their child in various life areas, including physical activities, well-being, cognition, social activities, behavior and general health during a specific time frame.

4. Study Design and Endpoints

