4.2.2 Secondary Study Endpoints

Evaluate changes from Baseline in cognitive, motor, and behavioral function as well as QOL following fenfluramine treatment.

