9.1 Statistical and Analytical Plans (SAP)

There will be no formal statistical methodology but rather descriptive statistics to quantify the primary and secondary outcome measures as well as the frequency and severity of adverse effects. All subjects participating in this study will have their data analyzed with descriptive statistics for both the primary and secondary analyses.

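### Does scoring the Global Impression of Change at Week 0, with an objective worded as change in impression, lead to one change score being subtracted from another?

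*Combined protocol and SAP*

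**What the plan says.** Section 7.4 defines the caregiver version as follows: "The parent/caregiver rated change on a 7-point scale: 1-very much improved; 2-much improved; 3-minimally improved; 4-no change", running on to 7 for the worst outcome. The investigator version uses the same anchors. Section 3.2 lists "Caregiver/Investigator Global Impression of Change (C/IGIC") first among the secondary objectives and gives the same anchors. The Endpoint row of the Protocol Summary does likewise.

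The schedule of activities marks C/IGIC at Weeks 0, 2, 6, 10 and 14, and again at extension visits. At Visit 1, section 7.5.1.1 lists "Caregiver and Investigator Global Impression of Change" among the assessments. Further down the same list comes "First dose given in office".

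The Objectives row of the Protocol Summary reads "Decrease in seizure frequency and change in impression and quality of life". Section 4.2.2 states the secondary endpoints as "Evaluate changes from Baseline in cognitive, motor, and behavioral function as well as QOL following fenfluramine treatment". Section 9.1 provides for "descriptive statistics to quantify the primary and secondary outcome measures", with no formal methodology.

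**The concern.** A change rating made before any drug has been given has no treatment period to describe, so the Week 0 score says nothing about fenfluramine. It nevertheless sits in the data beside Week 0 scores for QOLCE and PEDS-QL, where a baseline value is needed and subtraction is correct. The Objectives row pairs impression with quality of life under the single word change, and C/IGIC is the only impression measure in the protocol. An analyst who treated all three instruments alike would compute the post-dose C/IGIC minus the Week 0 C/IGIC. The result would no longer mean what the scale labels say. C/IGIC is listed first of three secondary outcomes and there are only 10 patients, so a distorted summary would be noticeable. Section 7.4 adds to the doubt by giving no comparison point for the rating.

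**Working it through.** The plan states no calculated figure for C/IGIC, so there is none to reproduce. The check sets the relevant texts side by side and adds a little scale arithmetic.

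**1. What the Week 0 rating can carry.** It is taken at the visit where dosing starts and is listed before the first dose. It therefore holds no treatment information.

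**2. Which texts bear on the summary method.**

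| Place | What it treats as the quantity of interest |
|---|---|
| Protocol Summary, Objectives row | Change in impression (one compressed phrase) |
| Protocol Summary, Endpoint row | The 7-point rating, with its labels |
| Section 3.2 | The 7-point rating, with its labels |
| Section 4.2.2 | Changes from Baseline in function and quality of life; C/IGIC not named |
| Section 7.4 | The 7-point rating; no difference score defined |
| Section 9.1 | Descriptive statistics on the outcome measures |

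One row can be read as a difference. The rows that define the outcome give the rating itself, and section 9.1 summarises the outcome measures so defined. The odd phrase is most simply read as a loose inversion of the instrument's own name.

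**3. What subtraction would do if someone did it.** Let R be a post-dose rating and R0 the Week 0 rating, with D = R − R0. The distance from the no-change anchor is R − 4. The two are equal only when R0 = 4. For R = 2 (much improved):

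- R0 = 4: D = 2 − 4 = −2, the correct distance.
- R0 = 2: D = 2 − 2 = 0.
- R0 = 6: D = 2 − 6 = −4.

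These R0 values are assumptions chosen to show the mechanism. The documents give no Week 0 distribution, so the number of patients affected cannot be estimated. Inclusion criterion 6 asks for at least 4 weeks of stable antiseizure treatment before screening. That does not force R0 = 4, but it gives no reason to expect widespread departures. Harm needs two things together: Week 0 scores other than 4, and a subtraction that the plan does not ask for.

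**4. How much collection is redundant.** Assume all 10 patients (section 9.2) complete the core visits. Then 5 visits × 2 raters × 10 patients = 100 ratings. Week 0 accounts for 1 × 2 × 10 = 20, leaving 100 − 20 = 80 post-dose ratings for the summary.

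**5. What depends on C/IGIC.** Entry to the extension rests on a reduction of at least 40% in convulsive seizures (sections 4.2.1, 7.5.1 and 7.5.2). There is no hypothesis test, and section 9.2 says the sample size was not derived statistically. No decision in the protocol uses the C/IGIC score.

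**The case for a change.** The strongest case for a change is that nothing forbids the subtraction. The objective literally says change in impression, a Week 0 score is on file, the neighbouring instruments are properly analysed as changes from Baseline, and section 9.1 is too brief to rule anything out. Taking Baseline as the raters' reference would not settle what happens to the Week 0 score. The edits would be short and would add no data collection.

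Part of this stands. The Week 0 rating has no stated use, and section 7.4 does not tell raters whether to compare with the state before treatment or with the previous visit. The second gap is more realistic than the subtraction. It matters most in the extension, where visits are 12 weeks apart and concomitant medication may change. An analyst cannot repair it after the event, because the reference is fixed when the rating is made. But section 4.2.2 makes Baseline the natural comparison in the core study, a single site collects all ratings, and the rater forms, which are not among the documents, may state the reference.

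The rest does not carry. That a method is not prohibited does not make it planned, and a form whose category 2 already means much improved gives an analyst no cause to subtract. Removing or flagging the Week 0 rating would leave every post-dose summary as it is.

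**Conclusion.** No change to the plan follows. The Week 0 C/IGIC is a redundant entry, and the Objectives phrase is most likely loose wording. Followed as written, the plan yields a descriptive summary of up to 80 post-dose core ratings, with up to 20 Week 0 ratings set aside. The effect on reported results is nil under that reading. A distorted result would need an unplanned subtraction as well as Week 0 scores other than 4. The missing comparison point in section 7.4 is a gap in detail for a descriptive secondary outcome in an open-label study of 10 patients, and it bears on no test or continuation decision.

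This rests on two assumptions: that the outcome is the rating as defined in section 3.2 and the Endpoint row, and that raters use the state before treatment as their reference, at least in the core study. The documents support the first directly. They make the second natural but do not state it.

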Endpoint	Primary outcome: Median monthly convulsive seizure frequency Secondary outcomes: 1. Caregiver/Investigator Global Impression of Change (C/IGIC). The parent/caregiver and investigator rated change on a 7-point scale: 1-very much improved; 2-much improved; 3-minimally improved; 4-no change; 5-minimally worse; 6-much worse; and 7-very much worse 2. Quality of Life in Childhood Epilepsy Scale (13). A low-burden parent/caregiver completed assessment that looks at how epilepsy affects day-to-day functioning of their child in various life areas, including physical activities, well-being, cognition, social activities, behavior and general health. 3. Pediatric Quality Of Life Inventory (PEDS-QL). A parent/caregiver completed assessment that looks at how epilepsy affects day-to-day functioning of their child in various life areas, including physical activities, well-being, cognition, social activities, behavior and general health during a specific time frame		
Study Duration	14 weeks with extension available		
Duration of IP administration	14 weeks with extension available		
Population	confirmed genetic/clinical diagnosis of CDKL5 Deficiency Disorder (CDD)		
Study Sites	1: NYU Comprehensive Epilepsy Center.		
Number of participants	10 patients: 7: ages 2-18 years old Max of 3: ages 18-35 years old		
Description of Study Agent	Liquid		
Key Procedures	Blood draws, questionnaires, Doppler echocardiogram, electrocardiogram		

Page 2 Study number: s18-01530

Version: 11 Jan 20									
Protocol Activity: Week (±7 days)	Baseline Week 0	Safety call	Week 2	Week 6	Safety call	Week 10	Safety call	Week 14	Post Taper Follow up
Visit	1	Safety call	2	3	Safety call	4	Safety call	5/End of study/ End of treatment/ Withdrawal visit	
Informed consent/assent	X								
Inclusion/exclusion criteria	X	X	X	X	X	X	X	X	
Medical history	X	X	X	X	X	X	X	X	X
Demographics	X		I	I.	I .	I	1	T	
Physical and neurological exam and Vital signs	X		X	X		X		X	
Adverse events	X	X	X	X	X	X	X	X	X
EKG	X			X				X	
Echo	X		37	X		37		X	
C/IGIC	X		X	X		X		X	
QOLCE PEDS-QOL	X		X	X		X		X	
Hematology & Chemistry (draw/handling) (CBC, CMP, LFTs, BUN, Creatinine), Coagulation	X		X	X		X		X	
HCG (urine and serum)	X		X	X		X		X	
THC (urine and serum)	X		X	X		X		X	
Urinalysis	X		X	X		X		X	
AED levels /Clobazam	X			X		X		X	
Study diary provided	X		X	X		X		X	
Study diary collected			X	X		X		X	
Study drug dispensed	X		X	X		X		X*	
Study Drug administration	X								

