4.2.3 Safety Endpoints

The safety endpoints the study are:

- Adverse events
- Laboratory safety (hematology, chemistry, coagulation, urinalysis)
- Vital signs (blood pressure, heart rate, temperature, and respiratory rate)
- Physical examination
- Neurological examination
- Questionnaires to measure changes in cognition of the subject
- 12-lead ECGs
- Doppler ECHOs
- Body weight

5. Study Enrollment and Withdrawal

All subjects and/or their parent/legal guardian must sign the appropriate informed consent prior to beginning any study-related activities, including Screening procedures. Additionally, an assent form should be signed by subjects age 7 to 17 years old, unless lacking capacity.

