During the routine visit, the investigator will inform each prospective subject/parent/legal guardian of the nature of the study, and explain the potential risks and study-related procedures. If the subject/parent/legal guardian agrees, they will be given the informed consent documents to read and sign prior to starting any study procedures. Only the Principal Investigator, sub-investigators, and other research personnel listed on the study will have access to subject information. Once the study subject/parent/legal guardian has signed the informed consent, the investigator will explain the study during the routine visit. If necessary, the investigator will inform the subject and surrogate that a capacity assessment will be performed to determine whether the subject is capable of providing an informed decision to participate in the study. At this time, a capacity assessment will be conducted if the subject does not refuse the assessment. Capacity will be assessed through neurological examinations and neuropsychology reports conducted by the physician as well as learning and/or development delays that have been documented. If there is already documentation of lack of capacity, no assessment will be needed. If it has been determined by the investigator that the subject has capacity, they will be given the assent form to review. The investigator will go over the study as described in the assent form including study visits and procedures. The subject will be allowed time to ask questions. If the subject is comfortable, then they can sign the assent. All documentation will be placed in the study binder and documented in the study visit note. A copy of the informed assent and consent documents will be given to the subject and the subject's parent/legal guardian. Screening procedures may begin. The Screening Period is 4 weeks, during which study candidates must complete a diary documenting the frequency and duration of seizures.

Refer to Section 7 for the Schedule of Events and specific requirements for each study visit.

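### The 4-week screening diary that Section 5.3 requires is missing from the visit schedule, which puts consent and first dose at one visit, and baseline seizure frequency is never defined

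*Combined protocol and SAP*

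**What the plan says.** Section 5.3 has the family sign consent before any study procedure and then sets the screening stage: "The Screening Period is 4 weeks, during which study candidates must complete a diary documenting the frequency and duration of seizures". The opening of Section 5 gives the same order, with consent signed "prior to beginning any study-related activities, including Screening procedures". Section 5.3 then hands over to the visit schedule: "Refer to Section 7 for the Schedule of Events and specific requirements for each study visit".

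Section 7.5.1.1 starts at Visit 1, Week 0. Its first item is "Obtain written informed consent/assent". The same visit tells the "caregiver to keep a seizure diary for the next 2 weeks", dispenses drug, and includes "First dose given in office". The schedule table in the Protocol Summary agrees: its first column is Week 0, which carries consent, diary provision and drug administration. The row "Study diary collected" is blank at Week 0 and first marked at Week 2.

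A baseline seizure frequency is needed in three places: the primary endpoint in Section 4.2.1 (median reduction in monthly convulsive seizure frequency), the 40% continuation rule in Sections 4.2.1 and 7.5, and the 75% efficacy criterion for Level 3 echocardiogram findings in Section 2.3.2. None of these gives a window, a data source or a calculation, and neither does Section 9.1.

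**The concern.** Section 5.3 puts at least four weeks of diary keeping between consent and first dose, while Section 7.5.1.1 lists both at one visit. The section that requires the diary defers to the section that leaves it out, so the instructions a site works from day to day have no step at which the pre-treatment diary is handed out, returned or checked.

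The study has no control group, so the reported reduction is only as good as the pre-treatment frequency it is measured against. If that diary is not kept before the first dose, it cannot be kept prospectively afterwards. Even where it is kept, nothing says that it is the baseline used for the endpoint. The analysis is descriptive in 10 patients, so no test, error rate or power is affected. What is at stake is the meaning of the reported reduction and of the percentages used for individual patients.

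**Working it through.** The plan gives no figure to reproduce here. The check sets the sections side by side and counts days from the schedule.

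**Order of events**

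| Step | Sections 5 and 5.3 | Schedule table and 7.5.1.1 |
|---|---|---|
| Consent | Before screening | Visit 1, Week 0 |
| Pre-treatment diary | 4 weeks, mandatory | Not listed |
| First diary listed | Screening diary | Issued at Visit 1, for the 2 weeks that follow |
| First diary collected | Not stated | Week 2 |
| First dose | Not placed | Visit 1, Week 0 |

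The table's visit window is ±7 days, which cannot absorb a gap of 4 × 7 = 28 days. The table and the visit text agree with each other, and the numbering runs from 7.5.1 straight to 7.5.1.1 (Baseline), so there is no sign of a lost screening subsection.

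**Scheduled diary days**, from the collection row of the table:

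- Weeks 0 to 2: 2 × 7 = 14
- Weeks 2 to 6: 4 × 7 = 28
- Weeks 6 to 10: 4 × 7 = 28
- Weeks 10 to 14: 4 × 7 = 28
- Total: 14 + 28 + 28 + 28 = 98 nominal days, all from the day of first dose onward

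The schedule itself therefore contains no pre-treatment diary days. The 28 days exist only in Section 5.3.

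**Can the scheduled diaries supply the baseline?** Not naturally. The Level 3 criterion contrasts seizures on treatment with baseline, and every scheduled diary is on treatment.

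**Can the screening diary supply it as described?** Not fully. Section 5.3 asks only for frequency and duration. The Visit 1 diary asks for "Seizure type and duration". The endpoint and inclusion criterion 7 count convulsive seizures, which requires the type.

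**Eligibility.** Criterion 7 requires at least 4 convulsive seizures per 4-week period. Eligibility is checked at Week 0, but the diary that could support that count has no scheduled collection by then.

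**The case against.** The strongest reply is that screening was plainly intended and the visit list is just incomplete. Section 7.5.1.1 itself records adverse events arising since consent was signed separately from those arising during the visit, which suggests that consent can come before Visit 1. Section 5.3 describes consent at a routine clinic visit. Inclusion criterion 6 counts back from screening, and Section 8.1 speaks of a baseline period for echocardiograms and ECGs. Section 5.3 is also binding text, and nothing in Section 7 waives it. On the baseline itself, only one pre-treatment diary is described and it lasts 4 weeks. Criterion 7 uses a 4-week unit, the Level 3 criterion uses 28 days, and the endpoint is monthly. There is one evident candidate and no rival.

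Much of this stands. It makes an incomplete schedule more likely than a design without a baseline. It does not remove the listing of consent and first dose at the same visit, supply a step that collects the diary, or link the diary to the endpoint.

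Three stronger readings are tempting and are not supported:

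- A reader might infer that patients will be dosed with no baseline data. That would happen only at a site that followed Section 7 and overlooked Section 5.3.
- A reader might infer that the 2-week diary contradicts the 4-week one. It covers the first interval on drug and is a different diary.
- A reader might infer from the 14 weeks of participation in Section 5.4 that screening was dropped. That figure also leaves out taper and post-taper follow-up, so it does not show this.

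**Conclusion.** The point holds as an inconsistency combined with a missing definition. The sections cannot all be followed as written: one set requires a 4-week diary between consent and treatment, and the other lists consent and first dose at one visit with no pre-dose diary step. All 98 scheduled diary days are on drug. Separately, the window and source of baseline convulsive seizure frequency are not stated anywhere, although that frequency is the primary endpoint's only comparator.

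The day count assumes nominal visit dates and takes the table and visit text at face value. How many patients, if any, would lack a pre-treatment diary cannot be derived from the documents, and neither can the size of any bias in the reported reduction. The matter should nevertheless be settled before patients are dosed, because a missed prospective baseline cannot be recovered.

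**What to change.** 1. Reconcile Section 5.3, the schedule table and Section 7.5.1.1 on the timing of consent and screening. Add a screening stage to the table and to Section 7.5 at which the diary already required by Section 5.3 is issued. At Visit 1, list its collection and review before the first dose, including for inclusion criterion 7.
2. Have the screening diary record seizure type as well as frequency and duration, so that convulsive seizures can be counted.
3. In Section 4.2.1, define the primary endpoint's baseline as convulsive seizures per 28 days from that pre-treatment diary.
4. The sponsor should reconcile how baseline is used in the 40% continuation rule (Sections 4.2.1 and 7.5) and the 75% Level 3 criterion (Section 2.3.2), and state what it means in each. The content of those clinical rules is for the sponsor, and no change to them is proposed here.

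The cost is protocol wording, one schedule column and one screening contact. The 4-week diary adds no new burden, since Section 5.3 already requires it.
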